informed, at the discretion of the PI, that his or her score is of concern. The Care Partner will be referred to appropriate services if deemed necessary (e.g., social worker or other counseling services). The other results will be provided, if asked, after all data is collected and analyzed.

b. Data and Specimen Banking

The video-recordings will ultimately be stored, indefinitely, in the Layton Center and ORCATECH Research Repository (IRB #6845). The video-recordings will show subjects' faces and their names, and any information discussed during the sessions and focus groups will be heard in the audio. Thus, the video-recordings will not be de-identified prior to repository storage. The researchers may use or share this information to conduct future research. Other researchers and those outside of OHSU (who are involved in conducting or overseeing research) may have access to the video-recordings as specified in the *"Privacy, Confidentiality, and Data Security"* section. To obtain this data, researchers must read the *Layton Center for Aging and Alzheimer's Disease Research Data Use and Disclosure and Authorship Policies*, then fill out the Layton Center's "Request for Research Data" form. This form is used across the Center for data requests. The form asks for the PI's information, project name and goals, and a signature (PI) agreeing to comply with the policies. The Data Core team, at the direction of the Data Core Lead ([name]) at the Layton Center reviews and approves these requests.

All scales will be de-identified and a participant number will be assigned to each scale for data management. All data will be kept on the limited-access drives or computers at OHSU or in a locked location in the Layton Center. Documents used for the intervention (Individual and Group Logs, Pre-treatment survey, Visit Information Sheet) will be stored with the interventionist and RA in a locked file or briefcase in the staff member's home. All documents will be shredded or returned to the Layton Center at the completion of the intervention. These documents will not contain any PHI, but will contain the participant's study ID #.

7. Privacy, Confidentiality, and Data Security

Standard institutional practices will be followed as described in the OHSU Information Security and Research Data Resource Guide to maintain the confidentiality and security of data collected in this study. Study staff will be trained with regard to these procedures.

To help us protect subjects' privacy, we have obtained a Certificate of Confidentiality from the National Institutes of Health. With this Certificate, the researchers can refuse to disclose information that may identify subjects, even by a court subpoena, in any federal, state, or local civil, criminal, administrative, legislative, or other proceedings. The researchers will use the Certificate to resist any demands for information that would identify subjects, except as explained below.

The Certificate cannot be used to resist a demand for information from personnel of the United States Government that is used for auditing or evaluation of federally funded projects or for information that must be disclosed in order to meet the requirements of the FDA. A Certificate of Confidentiality does not prevent subjects or members of subjects' families from voluntarily releasing information about them or their involvement in this research. If an insurer, employer, or other person obtains subjects' written consent to receive research information, then the researchers may not use the Certificate to withhold that information. However, if we learn about abuse of a child or elderly person or that a subject intends to harm him or herself or others, or about certain communicable diseases, we will report that to the proper authorities.

Upon enrollment, subjects will be assigned a code that will be used instead of their names, medical record number or other personally identifying information. However, video-recordings will show their faces and their first names and any information discussed during the sessions will be heard in the

audio. In this case, the information subjects give us will be identifiable as coming from them, and will not be private. Electronic files for data analysis will contain only the subject code. Codes will not contain any of the 18 HIPPA identifiers. The key associating the codes and the subjects personally identifying information will be restricted to the PI and study staff. The key will be kept secure on a restricted OHSU network drive in a limited access folder. Any paper files will be stored in the restricted-access offices at the Layton Center. Electronic data will be stored on restricted computers and/or drives on the OHSU network, to which access will require OHSU/ID password authentication.

This study will be using interactive, real-time delivery of telehealth care over distance using video-conferencing equipment. The basic mode of connectivity between the study subjects and the research team will be via OHSU's WebEx system. This platform is secure as independently validated by OHSU's IT and legal department.

The Webex recording system will be used to record the telehealth visits. This service can securely record all visits as needed. There is no limit as to how many visits can be recorded concurrently. Visit recordings will be managed through the Webex secure web portal requiring OHSU credentials and multi-factor authentication. OHSU Security Engineering department has agreed to ensure that this study's policies and procedures meet strict Information Security Directives (ISDs).

Video-recordings may be shared with other researchers and those outside of OHSU who are involved in conducting or overseeing research via the secure Webex portal, or via OHSU Box.com or OneDrive. Using Webex, video streaming links can be sent to identified users via email (which will require a password to access). Study coordinators can download the video files outright from the Webex portal and saved on OHSU's "X" drive in a highly secure, biometrically authenticated data center or shared via OHSU Box.com or OneDrive. Using OHSU Box.com or OneDrive the research team will use the "Invite Collaborators." To ensure the videos cannot be downloaded, the "Invitee Permissions" will be set at "Previewer."

Electronic survey data will be stored in a web-accessible server at Qualtrics or REDCap, though copies of this data will be transferred to a secure OHSU server via API call. Other electronic data will be stored on a secure, password protected OHSU server. Access to data is restricted to study personnel. Access to data requires username/password authentication.

8. Risks and Benefits

a. Risks to Subjects

There are few risks involved in this study. Care Partners will have to meet (via telehealth) with the research team for multiple visits, which may be inconvenient. Care Partners will need to find an activity for their care recipients during the sessions, which may cause financial hardship for some. All visits will be via telehealth, so there should be no travel costs involved.

Some of the questions on the scales may seem very personal or embarrassing and fatiguing to participants and may upset them. They may refuse to answer any of the questions that they do not wish to answer. If the questions make them very upset, we will refer them to a social worker. There is a risk that the video-recordings may be seen by someone they know. It is possible that someone viewing the videos may recognize them or their family members and/or hear their names in the audio, and their identities would no longer be confidential.

b. Potential Benefits to Subjects

Care Partners who complete all 8 training sessions may experience a reduction in their feelings of burden and depression. They may feel less likely to want to place their care recipients in long-term care. It is possible that these benefits will last up to 2 months. In general, they may feel better about caregiving. Care recipients may experience less psychological stress as their Care Partners learn to communicate and manage behaviors.

References

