a. Care Partners and Persons with Dementia. Up to 40 Care Partners and their 40 care-recipients with ADRD will participate in this study. The primary focus of this study is on Care Partners, however, we will gather subjective and objective data on participants with ADRD to assess the effect of the intervention on Care Partner affective responses to caregiving and quality of life for both. STELLA participants will be recruited from the existing cohort of patients, and their Care Partners, who are enrolled in the ORCASTRAIT Life Laboratory (OSLL).

There has been no pilot testing of STELLA with non-English speaking care partners, and all materials have been tested in English. Therefore, only English-speaking participants are included in STELLA.

b. Inclusion and exclusion criteria. The research team will assess eligibility of interested parties based on the criteria listed in Table 1. In the event of a screen failure, data collected during screening will be destroyed at the end of the study. The recruitment team will track the number of care partners contacted for the study, the number consented, the number of those that dropped out and the number of those that completed the entire intervention.

Table 1: Inclusion/Exclusion Criteria

Participant	Inclusion	Exclusion
Care Recipient	
 Diagnosis of ADRD, moderate to late stages Exhibits 2 or more behaviors listed on RMBPC¹⁶ that are bothersome to the Care Partner and occur 3 or more times/week at study enrollment Family member of Care Partner (this can be a relative, spouse or close kin that is considered family) 	
 Dementia not related to ADRD Unable to leave Care Partner during Partner training Early stage dementia, as defined by MoCA of about 15/30 or higher.

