Care Partner	
 Adult caring for family member with ADRD Lives with care recipient OR spends at least 4 hours/week with care recipient⁽²¹⁾ Age of 18 years or older Speak English Own a computer/device with a reliable internet connection and compatible operating system 	
 Unable to find activity for care recipient during training which would allow Care Partner to work privately, one-on-one during training Completed similar telehealth intervention within the last year Hearing and vision problems severe enough to prevent participation Unwilling or unable to adequately follow study instructions and participate in study procedures
Both	Participate in ORCASTRAIT (IRB#20236)	

c. Vulnerable populations. The primary focus of this study is to assess the feasibility, costs, and efficacy of subjective and objective measurements of Care Partner and person with dementia responses to the STELLA intervention. Therefore, in order for this study to be successful, participants with moderate to late stage ADRD will be recruited. Few interventions address the needs of families in these later stages.

We will ask that a legally authorized representative (LAR) and, if appropriate, the person with ADRD, if the person with ADRD is competent to make a decision about participation. If the LAR and/or the person with ADRD are concerned about competency, the LAR will be asked to make the participation decision. No other vulnerable populations such as children, prisoners, or pregnant women will be included in this study. All Care Partners will be 18 or older.

d. Setting. This study will take place at OHSU. Participants will connect (from their homes or another convenient location) to the research team via direct-to-home, telehealth, video-conferencing and over the telephone at the Layton Aging and Alzheimer's Disease Center. Interventionists will meet with

caregivers via videoconferencing on an OHSU computer and HIPAA secure link. The interventionist may complete the visit from his or her home, OHSU office or other convenient private location. They will use a privacy screen so that participants will not see their home or office environments. No others (e.g., family members of interventionists) will be allowed in the room during the intervention. Please see ORCASTRAIT (IRB#20236) protocol for details of living lab.

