This study requests a waiver of documentation of consent because subjects will have telehealth visits, which means they would have to make a trip to OHSU just to physically sign consent forms; this is unnecessarily burdensome. When the subjects verbally consent to participate in the study, the research team member who conducts the informed consent conversation will sign and date a copy of the information sheets, indicating that the forms were reviewed with the participants and that consent was obtained.

The person with ADRD may not have the cognitive function to understand the study or agree to consent. In this case, we will arrange for a LAR to consent for the person with ADRD. We will adhere to the standards set forth in the OHSU Guidelines for Decisionally Impaired Adults. Similarly, the Care Partner will also be asked to review and agree to the family member's information sheet. The information sheets will be discussed and consent will be obtained prior to the first visit (see *Consent - Information Sheet (Care Partner)* and *Consent – Information Sheet (Family Member)*).

The person with dementia will not partake in any STELLA activities, but we will analyze their data during the study period. Furthermore, our experience has taught us that some family members seek out their Care Partners during the video sessions. Thus, the person with dementia may be video-recorded. Therefore, we will seek the consent of the person with dementia, or their LAR's, to participate in this study.

5. Procedures Involved

Phase 1

Technology. Participants will be enrolled in the ORCASTAIT Life Lab (OSLL) enabling automatic generation of the full suite of digital biomarkers. As per the OSLL protocol, Care Partners and their family members with dementia both wear a long battery life (charged every 6 months) actigraph watch assessing activity (daily steps) and sleep patterns. Passive room sensors will provide activity location information (e.g., time out of home, time together).

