revised Desire to Institutionalize (DTI) scale.⁽²⁸⁾ Care Partner depression will be measured with the CESD-10⁽³⁰⁾ and role captivity will also be assessed.⁽³¹⁾ In addition to subjective assessments, we will evaluate the effect of STELLA on digital behavioral biomarkers (activity, time spent together and sleep) obtained from the ORCASTRAIT platform. Total daily activity, time together and alone, and sleep duration, will be assessed prior to, during, and after the intervention. Care Partners will complete all assessments electronically. A secure link to each assessment will be emailed to each CP. We will ask the CPs to complete the assessments within 5 days of receiving the email. If they do not, we will call them to assess their situation. If they do not complete surveys as outlined on the times listed in Table 3 they may not continue with the intervention.

Aim 3. To identify which components of STELLA are most helpful to Care Partners, we will assess the mechanisms of action for reducing burden, depression and grief and improving cognitive function and sleep. Care Partners will complete the surveys (**Table 3**) before the intervention, after Session 4 and after the intervention. An analysis of objective data (**Figure 1**) will also be done during the intervention. We will ask Care Partners in our focus groups to report what they found most helpful about STELLA.

Table 4: Subjective Assessment Descriptions

Measure	Description
Mercury Baseline	
Demographics	Demographics, including hours/week caregiving
Revised Memory & Behavioral Problems Checklist (RMBPC) ²³	Measure of frequency and reactivity to behavioral and psychological symptoms of dementia ²³
Personalized target problem assessment	Care partner-identified targeted problem assessment
Zarit Burden Interview (ZBI) ³³	4-item measure of burden
Center for Epidemiologic Studies Depression Scale (CESD-10) ³⁴	10-item depression measure
Marwit Meuser Caregiver Grief Index-Short Form (MMCGI-SF) ³⁵	Care partner pre-death grief ³⁵
Placement plan scale ³⁷	One-item assessment of plans for placement for family member with dementia ³⁷
QoL AD ³⁶	13-item assessment of quality of life for both the care partner and the person with dementia.
Starlet Survey	
ZBI ³³	
CESD-10 ³⁴	
Venus Survey	
RMBPC ²³	
 • See Baseline for descriptions • Baseline: 
 + STELLA contact survey + Experience Survey -Demographic survey
Personalized target problem assessment	

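### Co-resident and living-apart dyads are pooled in the unadjusted correlations of time together and time alone with burden, so those correlations could reflect living arrangement alone

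*Combined protocol and SAP*

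**What the plan says.** **Who can enter.** Table 1 (section 4) accepts a Care Partner who "Lives with care recipient OR spends at least 4 hours/week with care recipient". Both members of the dyad must also "Participate in ORCASTRAIT (IRB#20236"; the parent study's residence rules are not in this document. The planned size is stated as "Up to 40 Care Partners and their 40 care-recipients with ADRD will participate in this study".

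**How the sensor outcomes arise.** Section 5, Technology: "Passive room sensors will provide activity location information (e.g., time out of home, time together". Section 5, Measures, Aim 2: "Total daily activity, time together and alone, and sleep duration, will be assessed prior to, during, and after the intervention". Nothing defines time together or time alone for a dyad with two homes, or says which home carries the sensors.

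**How behaviour frequency arises.** Table 4 describes the RMBPC as "Measure of frequency and reactivity to behavioral and psychological symptoms of dementia". The Care Partner completes it, as with all the surveys. Entry also requires behaviours that are "bothersome to the Care Partner and occur 3 or more times/week at study enrollment".

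**How they are analysed.** Analytic Plan, Phase 1, Aim 2 does three things:
- It models change in the subjective scores by linear regression, with age, sex and education as the only covariates.
- It relates sensor means before, during and after the intervention to subjective data by simple Spearman correlation.
- It looks at each biomarker's shift from baseline.

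Co-residence enters none of these. The baseline survey does collect "Demographics, including hours/week caregiving", but no named model uses it, and Table 4 drops the demographic survey at Venus and Earth.

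**The concern.** Time together and time alone depend heavily on whether two people share a home. Burden may also depend on it. When two groups differ on both variables, pooling them produces a correlation even if the variables are unrelated inside each group. A Spearman correlation on period-mean levels is fully exposed to this.

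Aim 2 looks for sensor trends that go with burden, and Aim 3 uses objective and subjective results together to judge which parts of STELLA worked. A correlation produced by living arrangement could be taken as evidence that the digital measures track burden, and carried into the design of the next trial.

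RMBPC frequency has a related but weaker problem: what a Care Partner can report from direct observation depends on contact time.

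**Working it through.** **No figure to reproduce.** The plan gives no power, error-rate or expected-correlation figure for these analyses.

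**From the plan.** Up to 40 dyads. The contact floor is 4 hours a week: 4/168 = 2.4% of the week. This is the minimum allowed, not a description of the typical participant.

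**Assumed, because the documents are silent.**
- Share living apart: 5 to 50%.
- Burden higher in co-resident Care Partners by 0.2 to 0.8 SD.
- Weekly time together of 4 to 25 h in living-apart dyads and 50 to 112 h in co-resident dyads, uniform within each group.
- No relation between time together and burden within either group.

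**Simulation of the pooled Spearman, 40 dyads.** Each cell gives the mean correlation and the percentage of runs with two-sided p<0.05.

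| Living apart | Gap 0.2 SD | Gap 0.5 SD | Gap 0.8 SD |
|---|---|---|---|
| 5% (2 dyads) | 0.02; 5% | 0.04; 5% | 0.06; 6% |
| 10% (4) | 0.03; 6% | 0.08; 8% | 0.12; 10% |
| 25% (10) | 0.06; 7% | 0.15; 16% | 0.24; 33% |
| 50% (20) | 0.08; 8% | 0.21; 26% | 0.33; 55% |

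Repeat runs differ by about a percentage point. The distortion is negligible at 5%, small at 10%, and material from about 25% if the burden gap is 0.5 SD or more.

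**Does this depend on non-overlapping contact times?** No. Let both variables be normal, with living-apart dyads lower by dx SD on time together and dy SD on the score, and let p be the share living apart. The pooled Pearson correlation with no within-group relation is

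r = p(1−p)·dx·dy / √{[1 + p(1−p)dx²][1 + p(1−p)dy²]}.

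- p = 0.1, dx = 1, dy = 0.5: 0.045/√(1.09 × 1.0225) = 0.04.
- p = 0.5, dx = 2, dy = 1: 0.5/√(2 × 1.25) = 0.32.

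Simulated Spearman values at these two settings are 0.04 and 0.34, with p<0.05 in about 6% and 57% of runs.

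**Effect of adjusting.** In the first set-up, a partial Spearman adjusted for co-residence averages about zero and gives p<0.05 in about 5% of runs in every cell.

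**Change from baseline.** A stable living arrangement adds the same offset before and after, so it largely cancels. Correlating within-dyad relative change in time together with change in burden gave about 5% in every cell, provided change itself does not differ by residence.

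**The case against.** **The number of living-apart dyads may be small or zero.** Everyone must be in the parent study, whose rules are not available here. Care Partners must also find the care recipient something to do during sessions, and section 4 notes that some care recipients seek them out on video, which suggests substantial contact. This stands, and it makes the size conditional. It does not remove the point, because STELLA's own criterion expressly allows living apart and no analysis allows for it.

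**The study is exploratory.** The plan expects no statistically significant findings, so p<0.05 is only a gauge here and not the plan's decision rule. This stands; the harm is to interpretation.

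**Co-residence may be a real route to burden.** More time together through sharing a home could be a genuine exposure. This is fair, and it is a reason to show pooled and adjusted results side by side. The pooled figure alone cannot distinguish the two explanations.

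**Stronger readings that the documents do not support.**
- A reader might infer that time together registers only in one instrumented home and sits at floor or ceiling by residence. The documents do not say how it is derived.
- A reader might infer that the pre-post results are distorted too. They are largely protected, except where living arrangement changes during the 18 months of participation.
- A reader might infer that RMBPC frequency is invalid for living-apart dyads. Every dyad's frequency is Care Partner report, contact hours can change among co-residents too, and nothing shows that they do change.
- A reader might infer that living-apart dyads should be left out. That discards data when the feasibility of the objective monitoring is itself an aim.

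**Conclusion.** The point holds for the unadjusted correlations of period-mean sensor levels with subjective scores, chiefly time together, time alone and time out of home. Over the assumed ranges, a correlation due to living arrangement alone averages from about 0.02 (5% apart, 0.2 SD gap) to about 0.33 (50% apart, 0.8 SD gap). The proportion nominally significant runs from the expected 5% to about 55%. Where a study falls in that range depends on the share living apart and the burden gap, neither of which is documented. If burden were higher in living-apart Care Partners, the sign would reverse.

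This is a cheap improvement to the analysis plan. It is not a flaw in the eligibility rule, and it does not undermine the within-dyad change analyses while living arrangement is stable.

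**What to change.** Leave Table 1 as it is, and add the following:

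1. Carry co-residence forward from screening, where eligibility already requires it to be established, and ask it again at Venus and at both Earth surveys. Report how many dyads live apart and how many change.
2. Keep all dyads. Report the correlations of time together, time alone and time out of home with burden either by co-residence or as partial Spearman correlations adjusted for it, beside the pooled value. Baseline hours/week caregiving is an alternative adjuster, but it overlaps with time together and could remove real signal, so co-residence is the better first choice.
3. Add a co-resident-only sensitivity analysis of the same correlations.
4. Show RMBPC frequency change by co-residence as a descriptive breakdown.

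The cost is one repeated survey item, a few sentences of analysis text, and slightly less precision in the adjusted or stratified estimates. If nobody lives apart, the added analyses drop out.
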